9.7.3 Complete Response Rate

Complete response rate (CRR) will be defined as the proportion of patients with a best overall response of CR. The percentage of CRR with its 95% CI will be presented.

9.7.4 Relapse-free Survival

The RFS will be defined among CR patients as the time from the earliest date of first complete response until the first date of either disease relapse or death due to any cause. The date of disease progression will be defined as the earliest date of disease progression based on central review. For patients who have not progressed or died at the time of the analysis, censoring will be performed using the date of the last valid disease assessment. The data will be analyzed by the Kaplan-Meier method. The median DOR and 95% CI will be presented. Further details will be outlined in the SAP.

9.7.5 Progression-free Survival

The PFS will be defined among all-treated patients as the time from first dose of study drug until the first date of either disease progression or death due to any cause. The date of disease progression will be defined as the earliest date of disease progression based on central review. For patients whose disease has not progressed at the time of the analysis, censoring will be performed using the date of the last valid disease assessment. The data will be analyzed by the Kaplan-Meier method. The median PFS time and 95% CI will be presented. Further details will be outlined in the SAP.

9.7.6 Overall Survival

Median OS will be defined as the time from the first dose of study drug until death due to any cause. For patients who have not died at the time of the analysis, censoring will be performed using the date the patient was last known to be alive. The data will be analyzed by the Kaplan-Meier method. The median OS and 95% CI will be presented. Further details will be outlined in the SAP.

9.7.7 Patients Receiving Transplant

The fraction of patients receiving HSCT following camidanlumab tesirine, and without any other anticancer therapy in between other than the therapies preparing for HSCT, will be summarized.

9.8 Safety Analyses

Safety analyses will be presented descriptively.

9.8.1 Adverse Events

The focus of AE summarization will be on TEAEs. A TEAE is defined as an AE that occurs or worsens in the period extending from the first dose of study drug to 30 days after the last dose of study drug in this study or start of a new anticancer therapy/procedure, whichever comes earlier.

All TEAEs will be summarized. Summary tables will be presented to show the number of patients reporting TEAEs by severity grade and corresponding percentages. A patient who reports multiple TEAEs within the same Preferred Term (or System Organ Class) is counted only once for that Preferred Term (or System Organ Class) using the worst severity grade.

Separate summaries will be prepared for TEAEs classified as severe or life threatening (Grade 3 or higher); study drug-related AEs; AEs leading to treatment interruption, modification, or discontinuation; AESIs; serious AEs; and death.

9.8.2 Clinical Laboratory Results

Clinical hematology, coagulation panel, biochemistry, and urinalysis data will be summarized at each scheduled assessment. Shifts for clinical laboratory results that can be graded according to CTCAE v4.0 will be summarized by CTCAE grade. Shifts for other numeric laboratory results will be by high/normal/low flag. Shifts for all other laboratory results will be by normal/abnormal flag.

Summaries by visit will include data from scheduled assessments, and all data will be reported according to the nominal visit date for which it was recorded. Unscheduled data will be included in "worst-case post Baseline" summaries, which will capture a worst case across all scheduled and unscheduled visits after the first dose of study drug. Further details will be provided in the SAP.

9.8.3 Additional Safety Assessments

The results of scheduled assessments of vital signs, physical examinations, ECOG performance status, and 12-lead ECGs will be summarized. All data will be reported according to the nominal visit date for which it was recorded (i.e., no visit windows will be applied). Unscheduled data will be included in "worst-case" summaries, which will capture a worst case across all scheduled and unscheduled visits after the first dose of study drug. All data will be listed. Further details will be provided in the SAP.

9.9 Pharmacokinetic Analyses

The PK profile will include determination of maximum concentration (C_{max}), time to C_{max} (T_{max}), area under the concentration-time curve from time zero to the last quantifiable concentration (AUC_{last}), area under the concentration-time curve from time zero to the end of the dosing interval (AUC_{tau}), area under the concentration-time curve from time zero to infinity (AUC_{inf}), apparent terminal elimination half-life (T_{half}), clearance (CL), volume of distribution (V_{ss}), and accumulation index (AI).

PK parameters will be determined for all PK-evaluable patients using a non-compartmental population PK analysis using Phoenix WinNonlin (Certara US, Inc., Princeton, NJ, US) or other appropriate software. Supplemental integrated population PK analyses will be undertaken and reported separately to evaluate the population PK parameters for the typical patient and to identify covariate factors which influence drug disposition.

Potential correlations of PK parameters to Baseline characteristics and safety observations will be assessed but may be reported separately. In addition, the influence of camidanlumab tesirine PBD-conjugated antibody and unconjugated warhead SG3199 concentrations on the QTc interval will be assessed but reported separately.

9.10 Immunogenicity Analyses

A tiered immunogenicity strategy (Figure 3) will be undertaken to evaluate ADAs by screening and confirmatory assays with titer evaluation, followed by characterization and evaluation of neutralizing capacity as needed. ADA sample collection, banking, and testing in validated and to be validated assays will be according to the new Food and Drug Administration (FDA) Draft Guidance for Industry (April 2016): 'Assay Development and Validation for Immunogenicity testing of Therapeutic Protein Products'.

Screening Assay (Detection with whole ADC) Negative for ADA Positive for ADA Confirmatory Assay (competition with whole ADC) Negative for Positive for Titration Assay Titer Anti-ADC Anti-ADC (Detection with whole ADC) Domain Specificity Characterization Assays Neutralizing (Competition with mAb and BSA-SG3249 Assay Domain Specificity Positive for Anti-Non-neutralizing Neutralizing not Determined mAb or Anti-SG3249 Assess Impact on Safety, Efficacy, and PK

Figure 3 Anti-drug Antibody Tiered Immunogenicity Testing Strategy

Abbreviations: ADA, anti-drug antibody; ADC, antibody-drug conjugate; BSA, bovine serum albumin; mAb, monoclonal antibody; PK, pharmacokinetics.

Results from ADA testing will include tabular summarization for number/proportion of patients with positive predose ADA response, number of patients with postdose ADA response only, and number of patients with positive ADA response at any time. The denominator will be the total number of patients tested for ADAs in the study. For patients exhibiting a positive ADA, PK, safety and efficacy correlates will be assessed and reported.

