Pregnancy test, if applicable	7.4.6	X	On C1D1,		on D1 of every 6 wks apart)	other cycle (max.	X^6	

	Protocol Section	Screening	Treatment Period			Follow-up Period (up to 3 years from EOT)		
(1 Cycle = 21 days)			Cycle 1 and	Cycle 1 and Cycle 2 (C1 and C2) C3 a			EOT	Every 12 weeks (wks)
Day (D)		-28 to −1	1	8	15	1		
12-lead ECG	7.4.7 Table 3	X	X (Pre, EOI, Post)	X	X	C3 and C4 (Pre, EOI), C5 then every other cycle (Pre)	X	
Premedication	6.7.1		D-1 to D2			D-1 to D2		
Camidanlumab tesirine administration	6.3		X			X		
PK sample	7.5.1 Table 4		X (Pre, EOI, Post)	X	X	C3 through C6 (Pre, EOI), then every cycle (Pre)	X	
ADA sample	7.5.2 Table 4		X (Pre)		X C1 only	C3 (Pre), then every other cycle (Pre)	X^7	
Soluble biomarkers	7.5.3.1 Table 5		X (Pre, Post)	X	X	C3 (Pre, EOI), then every other cycle (Pre)	X	
cfDNA samples (gDNA only at C1D1 and EOT)	7.5.3.1		X (Pre)			6 and 12 weeks postdose (with disease assessment)	X	X at disease progression
HRQoL ⁸	7.6		X			X	X	
Concomitant medications ⁹	6.8	Fro	From ICF signature date or D-14, whichever is earlier, until 30 days after last dose of study drug					
Adverse events	8	AE/SAE	AE/SAEs from ICF signature date until 30 days after last dose of study drug; thereafter, related SAEs only					
1 st New anticancer treatment	4.2.3						X	X
Survival	4.2.5						X	X

Abbreviations: ADA, anti-drug antibody; AE, adverse event; BP, blood pressure; cfDNA: circulating cell-free DNA; ECG, electrocardiogram; ECOG, Eastern Cooperative Oncology Group; EOI, end of infusion; EOT, end of treatment; HR, heart rate; gDNA, genomic DNA; HRQoL, health-related quality of life; ICF, informed consent form; PK, pharmacokinetics; post, postdose; pre, predose; RR, respiratory rate; SARS-CoV-2: respiratory syndrome coronavirus 2; SAE, serious adverse event; Temp, temperature; VZV, varicella zoster virus.

- Screening imaging must be performed within 4 weeks prior to C1D1 and the same assessment method should be used throughout the study. Week 6 imaging should be performed within 1 week prior to C3D1 and Week 12 imaging should be performed within 1 week prior to C5D1. All other imaging for disease assessment for patients on study drug should be performed within ±2 weeks of the scheduled timepoint. Disease assessments should be performed at the timepoints specified even if study drug dosing is delayed. If a scan has been performed within 6 weeks of EOT, it does not need to be repeated at EOT.

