Characterize additional efficacy endpoints of camidanlumab tesirine	 DOR defined as the time from the first documentation of tumor response to disease progression or death CR rate defined as the percentage of treated patients with a best overall response (BOR) of CR Relapse-free survival (RFS) defined as the time from the documentation of CR to disease progression or death Progression-free survival (PFS) defined as the time from first dose of study drug until the first date of either disease progression or death due to any cause Overall survival (OS) defined as the time from first dose of study drug until death due to any cause Fraction of patients receiving hematopoietic stem cell transplant (HSCT).
Characterize the safety profile of camidanlumab tesirine	 Frequency and severity of AEs and SAEs Changes from Baseline of safety laboratory values, vital signs, Eastern Cooperative Oncology Group (ECOG) performance status, and 12-lead electrocardiograms (ECGs)
Characterize the PK profile of camidanlumab tesirine	 Concentrations and PK parameters of camidanlumab tesirine total antibody, PBD-conjugated antibody, and unconjugated warhead SG3199
Evaluate the immunogenicity of camidanlumab tesirine	• Frequency of confirmed positive anti-drug antibody (ADA) responses, their associated ADA titers and, if applicable, neutralizing activity to camidanlumab tesirine after treatment with camidanlumab tesirine

Objectives	Endpoints
Evaluate the impact of camidanlumab tesirine treatment on health-related quality of life (HRQoL)	 Change from Baseline in HRQoL as measured by EuroQoL-5 Dimensions – 5 Levels (EQ-5D-5L) and Functional Assessment of Cancer Therapy – Lymphoma (FACT-Lym)
Exploratory	
Assess the pharmacodynamic effects of camidanlumab tesirine	• Changes in levels of immunologically relevant biomarkers in blood such as but not limited to IL-2, IL-10, and soluble CD25 (sCD25)
Characterize tumor and tumor-associated non-tumor cells (TANT), as well as immunological relevant parameters in tumor tissue	 Measurement of CD25(+) tumor cells and TANT in baseline tumor tissue Measurement of tumor infiltrating lymphocytes (TILs) and other immunologically relevant parameters in baseline tumor tissue

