5.2 Exclusion Criteria

- 1. Previous treatment with camidanlumab tesirine.
- 2. Participation in another investigational interventional study. Being in follow-up of another investigational study is allowed.
- 3. Known history of hypersensitivity to or positive serum human anti-drug antibody (ADA) to a CD25 antibody.
- 4. Allogenic or autologous HSCT within 60 days prior to start of study drug.
- 5. Active graft-versus-host disease (GVHD), except for non-neurologic symptoms as a manifestation of mild (≤ Grade 1) chronic GVHD.
- 6. Post-HSCT lymphoproliferative disorders.

- 7. Active second primary malignancy other than non-melanoma skin cancers, non-metastatic prostate cancer, in situ cervical cancer, ductal or lobular carcinoma in situ of the breast, or other malignancy that the Sponsor's medical monitor and Investigator agree and document should not be exclusionary.
- 8. History of symptomatic autoimmune disease (e.g., rheumatoid arthritis, systemic progressive sclerosis [scleroderma], systemic lupus erythematosus, Sjögren's syndrome, autoimmune vasculitis [e.g., Wegener's granulomatosis]) (subjects with vitiligo, type 1 diabetes mellitus, residual hypothyroidism, hypophysitis due to autoimmune condition only requiring hormone replacement may be enrolled).
- 9. History of neuropathy considered of autoimmune origin (e.g., polyradiculopathy including Guillain-Barré syndrome and myasthenia gravis) or other central nervous system autoimmune disease (e.g., poliomyelitis, multiple sclerosis).
- 10. History of recent infection (within 4 weeks of C1D1) considered to be caused by one of the following pathogens: HSV1, HSV2, VZV, EBV, CMV, measles, Influenza A, Zika virus, Chikungunya virus, mycoplasma pneumonia, *Campylobacter jejuni*, enterovirus D68, or severe acute respiratory syndrome coronavirus 2 (SARS-CoV-2).
 - Note: An influenza test and a pathogen-directed SARS-CoV-2 test (such as polymerase chain reaction [PCR]) are mandatory and must be negative before initiating study treatment (tests to be performed 3 days or less prior to dosing on C1D1; an additional 2 days are allowed in the event of logistical issues for receiving the results on time).
- 11. Patients who are carriers of human immunodeficiency (HIV) virus, hepatitis B virus (HBV), or hepatitis C virus (HCV), and require anti-viral therapy or prophylaxis.

 Note: Serology testing is mandatory for patients with unknown status.

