7.5.1 Pharmacokinetics

The PK profile of camidanlumab tesirine PBD-conjugated antibody, total antibody, and unconjugated warhead SG3199 will be assessed in serum by a central laboratory designated by the Sponsor using validated bioanalytical methods.

Up to 6 mL of whole blood will be collected as per Table 1 and Table 4. Blood should be drawn from a vein away from the one used for study drug infusion.

The serum PK samples must be stored at \leq -70°C. Please refer to the laboratory manual for detailed instructions regarding specimen handling and shipment.

At timepoints coinciding with ECG collection, PK blood collection should occur immediately after the end of the ECG recording and, when applicable, after vital signs (example in Figure 2). If a patient experiences Torsade de Pointes, concomitant PK samples (e.g., unscheduled) should be collected.

Table 4 Sampling Schedule for PK and ADA

Cycle	Day	PK timepoint (window)	ADA timepoint (window)
C1	D1	Predose (preferably within 2 h prior to start of infusion)	Predose (preferably within 2 h prior to start of infusion)
		EOI (-5 to +10 min) Postdose* 4 h (± 10 min)	
	D8	Postdose* 168 h (± 48 h)	-
	D15	Postdose* 336 h (± 48 h)	Postdose* 336 h (± 48 h)
C2	D1	Predose (within 2 h prior to start of infusion)	Predose (within 2 h prior to start of infusion)
		EOI (-5 to +10 min)	
		Postdose* 4 h (± 10 min)	
	D8	Postdose* 168 h (± 48 h)	-
	D15	Postdose* 336 h (± 48 h)	-
C3, C4, C5, and C6	D1	Predose (within 2 h prior to start of infusion)	-
		EOI (-5 to +10 min)	
C3, C5,	D1	-	Predose (within 2 h prior to start of
every other cycle			infusion)
C7, C8,	D1	Predose (within 2 h prior to start of	-
every cycle		infusion)	

Cycle	Day	PK timepoint (window)	ADA timepoint (window)
ЕОТ		At any time during visit day	At any time during visit day
Unscheduled			Any time (if applicable, together with PK sample)

Abbreviations: ADA, anti-drug antibody; EOI, end of infusion; EOT, end of treatment; PK, pharmacokinetics.

To understand the metabolic disposition of camidanlumab tesirine in humans, samples remaining after PK analysis is complete may be pooled among patients for potential metabolite identification.

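### The post-dose-only ADA rate is divided by all patients tested, some of whom cannot have that outcome, so it is understated whenever such patients and any post-dose-only positive exist.

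*Protocol*

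**What the plan says.** Protocol 9.10 lists three ADA summaries: the number or proportion of patients positive pre-dose, and then the "number of patients with postdose ADA response only, and number of patients with positive ADA response at any time". One sentence sets the denominator, without limiting it to any one row: "The denominator will be the total number of patients tested for ADAs in the study".

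The related secondary endpoint, in Protocol Section 3 (Table 2), covers the frequency of confirmed positive ADA responses, their titers and, if applicable, "neutralizing activity to camidanlumab tesirine after treatment with camidanlumab tesirine". I read the closing reference to treatment as applying to the whole endpoint.

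ADA sampling is set out in Protocol Tables 1 and 4. The first draw is pre-dose on Cycle 1 Day 1. Post-dose draws follow on Cycle 1 Day 15, before dosing in Cycles 2 and 3, before dosing in every other cycle after that, and at EOT. Unscheduled samples are allowed.

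Exclusion criterion 3 (Protocol 5.2) bars patients with "Known history of hypersensitivity to or positive serum human anti-drug antibody (ADA) to a CD25 antibody".

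Protocol Section 9 leaves full analysis details to the SAP. The SAP names immunogenicity as an objective (2.2) but has no ADA analysis section. It defines no ADA population among those in 4.1 and records no modification to the protocol's statistical section (3.3). The rule in Protocol 9.10 therefore stands.

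**The concern.** A rate of new post-dose positivity should be taken over patients who could show it. Two groups in the stated denominator cannot:

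- patients with no post-dose ADA result, who are tested only in the sense that a pre-dose sample exists;
- patients already positive pre-dose, who by definition cannot be in the "number of patients with postdose ADA response only".

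Both groups can push this rate only downward. In the rate as written, a patient never sampled after dosing has the same effect as one sampled and found negative, and the planned table does not show how many patients are in that position.

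The plan applies the sounder principle elsewhere. The PK Population (Protocol 9.2) needs a pre-dose and a post-dose assessment, and the PRO Population (SAP 4.1.5) needs a baseline and a post-baseline score. ADA has no equivalent.

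At stake is the accuracy of one descriptive secondary safety result. No hypothesis test, threshold or decision rule in the plan uses it.

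**Working it through.** The documents state no ADA incidence, no count of missing samples and no pre-dose positivity, so there is no ADA figure to reproduce. The check is proportion arithmetic with assumed counts, on the scale of the planned sample size of 100 (Protocol 9.1).

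**Definitions**

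- N = patients tested for ADA, each assumed to have a pre-dose result.
- x = post-dose-only positives.
- m = patients with no post-dose result.
- b = pre-dose positives who have a post-dose result.

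**Post-dose-only row**

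- Rate as planned: x / N.
- Rate among patients at risk (negative pre-dose, with a post-dose result): x / (N − m − b).
- Planned rate = at-risk rate × (N − m − b) / N, so the relative understatement is (m + b) / N.

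The two rates agree if m + b = 0. If m + b > 0 and x > 0, the planned rate is lower. It cannot be higher from this cause.

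With N = 100 (all values of x, m and b are assumptions):

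| m | b | At risk | x = 2 | x = 5 | x = 10 | Relative understatement |
|---|---|---|---|---|---|---|
| 0 | 0 | 100 | 2.00% | 5.00% | 10.00% | 0% |
| 2 | 2 | 96 | 2.08% | 5.21% | 10.42% | 4% |
| 5 | 5 | 90 | 2.22% | 5.56% | 11.11% | 10% |
| 10 | 10 | 80 | 2.50% | 6.25% | 12.50% | 20% |

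The first line also gives the planned rate in every scenario.

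**Any-time row.** Pre-dose positives are in both numerator and denominator, so they do not dilute it. Only patients without a post-dose result can. With x = 5, m = 5 and b = 5, and with the five patients lacking a post-dose result all negative pre-dose, the planned rate is (5 + 5)/100 = 10.0%. Among patients with a post-dose result it is (5 + 5)/95 = 10.5%.

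**Pre-dose row.** If every tested patient has a pre-dose result, N is the right denominator and nothing changes.

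**What limits m and b.** A patient who stops after one dose is still asked to attend EOT (Protocol 5.5.1), preferably within 30 days of the last dose (4.2.3), and an ADA sample is scheduled there. So m holds only patients with no post-dose draw at all, for example through early death, withdrawal of consent, loss to follow-up or a missed EOT visit. Exclusion criterion 3 keeps b low but not necessarily zero, because it covers known positivity only. The plan itself tabulates pre-dose positives.

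**The case against.** The best defense is that one denominator is a legitimate descriptive choice. Pre-dose positives plus post-dose-only positives make up the any-time positives, so the three rows add up. The pre-dose-positive count is in the same table, so a reader can remove those patients. This stands as a reason to keep the all-tested table. It does not answer the other half of the problem, because the number with no post-dose sample is not shown and the reader cannot correct for it.

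It can also be said that 9.10 attaches a proportion explicitly only to the pre-dose row. That is true, but the denominator sentence is not limited to that row and no other denominator is given. A post-dose-only percentage over all tested is the natural reading, though an inferred one.

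The effect is also small against sampling error. The exact 95% interval for 5/100 is about 1.6% to 11.3%, and every x = 5 value in the table lies well inside it. That limits the importance of the point but does not justify a rule that can err in only one direction.

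Three stronger readings are tempting, and the documents do not support them:

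- A reader might infer that everyone who leaves before Day 15 is counted as ADA-negative without a post-dose test. The scheduled EOT sample covers many of these patients, and 9.10 does not say that patients without a post-dose sample are classed as negative.
- A reader might infer that the immunogenicity result as a whole is understated. The effect differs by row, and it is zero if everyone has a post-dose result and no one is positive pre-dose.
- A reader might infer that the endpoint means treatment-induced ADA in baseline negatives. Table 2 does not restrict it so, and a pre-dose-positive patient can still test positive after treatment. The case for removing pre-dose positives therefore applies to the post-dose-only row, not to the endpoint in general.

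**Conclusion.** The point holds for the post-dose-only rate. As written, it is understated by the fraction (m + b)/N whenever patients without a post-dose result or with pre-dose positivity exist and any post-dose-only positive occurs. The any-time rate is affected only through patients with no post-dose result, and the pre-dose rate is not affected in this way.

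The direction follows from the definitions. The size does not follow from anything in the documents, and the assumed scenarios run from no change to a 20% relative understatement. Given the EOT sample and exclusion criterion 3, the lower part of that range is more plausible. This is a minor, easily corrected flaw in a descriptive secondary analysis.

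There is one related gap. The three listed counts have no category for patients positive pre-dose whose titer rises after dosing, so such a rise would appear in no treatment-emergent count.

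**What to change.** In Protocol 9.10 or a new SAP section on immunogenicity, define an ADA-evaluable set: patients with a pre-dose result and at least one post-dose result. Then report:

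- pre-dose positivity over patients with a pre-dose result;
- post-dose-only (treatment-induced) ADA over ADA-evaluable patients who were negative pre-dose;
- any post-dose positivity over patients with at least one post-dose result;
- titer increase among ADA-evaluable patients who were positive pre-dose, with the size of increase that counts stated in advance;
- the number of patients with no post-dose sample.

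The all-tested table can be kept alongside.

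The cost is a short addition to the text. No new sample, visit or patient is needed, because the data are already scheduled. The drawbacks are a slightly higher reported ADA rate and rows that no longer share one denominator.
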